7.1.1.1.2. Single Imputation Method

The single imputation method was the method used for previously submitted studies. It is being provided in this study as a bridge to the older studies.

For calculation of area under the curve (AUC) of NRS pain intensity scores, the windowed worst observation carried forward (wWOCF) and last observation carried forward (LOCF) imputation procedure will be used in the following order:

- a) Windowed worst observation carried forward for rescue medications

For subjects who take a rescue medication, their NRS scores recorded within the window of controlled type of rescue medication (see Table 2) will be replaced by the 'worst' observation. The worst observation will be the highest score in the time interval from time 0 up to the time of first rescue medication. The NRS score at the first rescue will be included in this calculation. Note that NRS scores in the window that are higher than the worst value prior to rescue medication will not be overwritten. If no NRS score is available prior to the first rescue the worst observation from all available NRS scores for that subject will be used instead.

- b) Missing scores before the first non-missing score will be replaced by the median score at the missing time point from the other subjects in the same treatment group.
- c) Missing scores after the last non-missing score will be replaced by the LOCF.
- d) Missing scores between two non-missing scores will not be replaced (i.e., linear interpolation will be used).
- e) Subjects who have no pain intensity scores recorded after surgery will have the missing scores replaced by the median score at each time point from all subjects in the same treatment group.
- f) The AUC and SPIS at various time intervals will be derived from the imputed NRS scores resulting from Step e.

7.1.1.2. Integrated Rank Assessment

No imputation of missing data will be performed for the integrated rank assessment calculation. Subjects with missing NRS scores at the timepoints of interest will not be included in the summaries.

7.1.1.3. Surgery Date or Time

It is expected that all necessary information on surgery (start and stop date and time) and postsurgical rescue medication (start dates and times, doses, frequency) will be complete. Any such information that is missing and cannot be obtained through query resolution may be imputed, on a case-by-case basis, in a conservative manner that minimizes bias. For example, if pain medication taken on Day 1 has no time of administration recorded, the imputed time will be the end of surgery.

7.1.1.4. Rescue Pain Medication

For calculation of the total rescue pain medication usage (in morphine dose equivalent) through a time point, if a subject is discontinued early (e.g., dies, withdraws consent, is withdrawn from the study, or is lost to follow-up) before the end of the time interval (e.g., 24 hours after study drug administration), his or her total rescue pain medication usage through the time interval will be a projected amount. For example, if a subject discontinues early at 6 hours after surgery, the projected amounts through 24 hours will be actual amount + average amount (actual amount/6 hours) multiplied by the number of hours remaining in the time interval (18=24-6).

7.1.1.5. Adverse Event or Concomitant Medications Dates or Times

For AEs or concomitant medications with missing or partially missing start/stop date/time, the following imputation rules will be applied:

For partial start date/time:

- If the year is unknown, then the date will be assigned the date and time of first dose of study treatment.
- If the month is unknown, then:
 - i) If the year matches the year of the dose of study drug date, then the month and day of the dose of study drug date will be imputed.
 - i) Otherwise, 'January' will be assigned.

- If the day is unknown, then:
 - i) If the month and year match the month and year of the dose of study drug date, then the day of the dose of study drug date will be imputed.
 - ii) Otherwise, '01' will be assigned.
- If the time is unknown, then:
 - iii) If the date (day, month, and year) matches the date of the administration of study drug, then the time of the dose of study drug time will be imputed.
 - iv) Otherwise, '00:00' will be assigned.

For partial stop date/time:

- If the year is unknown, then the date assigned will be the date subject discontinued from study, time will be set to the last time of the day ('23:59').
- If the month is unknown, then month subject discontinued from study will be assigned.
- If the day is unknown, then the last day of the month will be assigned.
- If the time is unknown, then the last time of the day will be assigned ('23:59').

7.1.1.6. Adverse Event Severity or Relationship to Study Drug

If severity of an AE is not reported, then for tables of AEs by severity, the event will be classified as 'Severe'. If relationship to study drug is not reported for an AE, then for tables of study-drug related AEs, the event will be assigned the relationship of 'definite'. Tables presenting related AEs will include all AEs with relationships of 'possible', 'probable' or 'definite' as assessed by the investigator

7.1.1.7. Time to Event

For calculating time to an event when only the hour is reported, the minutes will be set to zero. If only date is reported, the time will be set to midnight (00:00).

7.1.2. Multiplicity Adjustments

Since no multiple comparisons of the primary efficacy endpoint will be made, no alpha-adjustments will be made.

Also, since there is only one primary efficacy endpoint and all other efficacy endpoints are considered secondary or tertiary, no alpha-adjustments for the primary response variable will be made.

There are five secondary efficacy endpoints that will be analyzed using a hierarchical fixed-sequence stepwise testing procedure (See Section 7.6.1.2). The five secondary efficacy endpoints will only be analyzed if the primary efficacy endpoint is statistically significant at the two-sided 0.05 significance level. To protect the Type 1 error rate, the testing will be performed sequentially rejecting secondary endpoints at the two-sided 0.05 significance. The prior secondary endpoint must be rejected before proceeding to the next. The five secondary endpoints will be tested in the following order:

1. AUC(0.25-24)
2. AUC(0.25-72)

3. Percentage of opioid-free subjects from end of surgery through 24 hours
4. Percentage of opioid-free subjects from end of surgery through 48 hours
5. Percentage of opioid-free subjects from end of surgery through 72 hours

Tertiary efficacy endpoints will be summarized but not be analyzed.

7.1.3. By-Site Analyses

By-site summaries will present descriptive statistics only; no statistical analyses will be performed for individual sites. By-site summaries will be presented for disposition, demographics, primary efficacy endpoint and secondary efficacy endpoints.

7.2. Subject Disposition

Subject disposition summaries will include the number of subjects that were:

- Screened,
- Randomized
 - Randomized Not treated,
 - Randomized Treated,
- In the safety analysis set,
- In the primary efficacy analysis set,
- In the secondary efficacy analysis set
- In the PK analysis set,
- Completed the study as planned,
- Discontinued from the study, and
- Reasons for discontinuation from the study.

Percentages will be reported for the safety, efficacy and PK analysis sets, completed study, discontinued from study and reasons for discontinuation. The denominator for all percentages will be the number of subjects randomized.

Safety and PK analysis sets will be presented as treated. This may result in percentages greater than 100%. All other data will be presented as randomized.

Summaries will present the data for each treatment group (EXPAREL, Placebo) and across treatment groups (Total). This summary table will show summaries across all sites and for each site separately.

7.3. Description of Demographics

The summary of demographics will present:

- Age (years) – descriptive statistics
- Sex – n (%)
- Ethnicity – n (%)
- Race – n (%)
- Height (cm) – descriptive statistics
- Weight (kg) – descriptive statistics
- Body Mass Index (BMI) (kg/m²) – descriptive statistics

Age is calculated from the date the subject signed the ICF and birth. It is presented as the number of years between, rounding down to the nearest integer year.

The formula for BMI is $w/(h^2)$, where w is weight in kilograms and h is height in meters. Weight in pounds will be converted to kilograms using the conversion factor of 2.2046 pounds to 1 kilogram. Height in inches will be converted to centimeters using the conversion factor of 2.54 centimeters to 1 inch. Height in centimeters will be converted to meters using the conversion factor of 100 centimeters to 1 meter.

Summaries will present the data for each treatment group (EXPAREL, Placebo) and across treatment groups (Total). Summaries will be provided for all (safety, efficacy and PK) analysis sets. This summary table will show summaries across all sites and for each site separately.

7.4. Prior and Concomitant Medications

Prior and concomitant medications will be coded using the World Health Organization Drug Dictionary (WHO-DD) and will be classified according to the default anatomical therapeutic chemical (ATC) classification system term and preferred name.

Prior medications are defined as medications with a stop datetime prior to end of surgery. Concomitant medications are defined as medications taken after the start of study drug administration (i.e., started prior to the start of study drug administration and continued after or started after the start of study drug administration).

Prior and concomitant medications will be summarized separately using n (%) of subjects for each treatment group and across treatment groups by ATC class term and preferred name for the safety analysis set. Subjects may have more than one medication per ATC category and preferred name. At each level of subject summarization, a subject will be counted once if one or more medications are reported by the subject at that level.

A listing mapping the ATC term and preferred name to verbatim term will be presented.

7.5. Measurements of Treatment Compliance

Study treatment is administered by a party other than the subject, therefore compliance is assured. Duration of surgery will be summarized by treatment and across treatments.

7.6. Efficacy Analysis

Primary and secondary efficacy endpoints will be summarized and analyzed using inferential statistics. Tertiary efficacy endpoints will be summarized, no statistical tests will be performed on these endpoints.

7.6.1. Efficacy Endpoints

7.6.1.1. Primary Efficacy

The primary endpoint is the AUC of the NRS pain intensity scores through 48 hours [AUC(0.25-48)].

7.6.1.2. Secondary Efficacy

The following secondary endpoints will be analyzed in the following order using a hierarchical fixed-sequence stepwise testing procedure:

1. The AUC of the NRS pain intensity scores through 24 hours [AUC(0.25-24)].
2. The AUC of the NRS pain intensity scores through 72 hours [AUC(0.25-72)].
3. Percentage of opioid-free subjects from end of surgery through 24 hours.
4. Percentage of opioid-free subjects from end of surgery through 48 hours.
5. Percentage of opioid-free subjects from end of surgery through 72 hours.

7.6.1.3. Tertiary Efficacy

- The AUC of the NRS pain intensity scores through 96 hours.
- Sum of pain intensity scores (SPIS) through 24, 48, 72, and 96 hours.
- The NRS pain intensity scores at each assessed timepoint and immediately prior to each request for rescue pain medication.
- The AUC of the NRS pain intensity scores from 24-48 and 48-72 hours.
- Percentage of pain-free subjects at each assessed timepoint using the NRS pain intensity score.
- Percentage of opioid-free subjects through 96 hours.
- Time to first opioid rescue medication.
- Integrated rank assessment using the NRS pain intensity score at 48 hours and the total amount of postsurgical opioids consumed through 48 hours (Silverman 1993)⁸.
- Overall assessment of the subject's satisfaction with postsurgical pain control (using a 5-point Likert scale) at 24, 48, 72, and 96 hours, and on Day 10.
- PoSSe scale mean total score at 72 hours and on Day 7.
- Number of unscheduled phone calls or office visits related to pain through Day 30.

7.6.1.4. Opioid Consumption

Opioids will be converted to IV Morphine Equivalent Dose (MED) using the appropriate conversion factor from [Table 3](#) for all summaries. Total opioid dose (MED) is the sum of all opioids taken after surgery up to the timepoint of interest. Subjects with no opioid use during the period in question will be assigned a dose of 0 for analysis.

Table 3: IV Morphine Equivalents

| Medication | Unit | Route | Conversion (Multiplication) Factor |
|---|------|-------|------------------------------------|
| Oxycodone | mg | PO | 0.5 |
| Opioids taken during the study not on table will be reviewed and conversion factor determined. | | | |

7.6.1.5. Area Under the Curve

Area under the pain-time curve is derived using the trapezoidal rule on the pain scores adjusted for rescue medication use using the wWOCF imputation methods (see Section [7.1.1.1](#)). Actual

assessment times will be used in deriving AUC. AUC of pain scores will be calculated from the first timepoint after surgery to the timepoint of interest.

7.6.1.6. Sum of Pain Intensity Scores

The sum of pain intensity scores (SPIS) is the sum of the pain scores from the first timepoint after surgery to the timepoint of interest. The pain scores obtained after wWOCF imputation method will be used to derive SPI. SPIs will be derived for 24, 48, 72 and 96 hours.

7.6.1.7. Integrated Rank Assessment

Integrated rank assessment is a single score that takes pain rating and rescue medication use into account. Positive values for the integrated rank assessment score indicate less pain or opioid use and negative numbers indicate more pain or opioid use. The score is derived as:

$$\left[\frac{2r - p_i - m_i}{r} \right] * 100$$

Where:

- i indicates subject;
- p_i is the rank of the subject's pain score in the pool of all subjects to be analyzed;
- m_i is the rank of the subject's total opioid use (in MED) through the time period in question in the pool of all subjects to be analyzed;
- r is the mean rank defined as $(N + 1)/2$;
- N is the total number of subjects to be analyzed.

Subjects with no opioid use will be assigned a dose of 0 for analysis.

Integrated rank assessment will be calculated at 24, 48 and 72 hour timepoints. Missing NRS scores at timepoints of interest will not be imputed. Subjects with missing NRS values at the timepoint of interest will be excluded from the summary. If the timepoint of interest falls within a rescue medication window, the wWOCF value will be used to derive the integrated rank assessment.

7.6.1.8. Postoperative Symptom Severity (PoSSe) Questionnaire

The PoSSe score is the total score of the weighted responses for each question. If a response is missing to any question in the PoSSe, the total score will not be calculated.

7.6.1.9. Time to First Opioid Rescue Medication Use

Time to first opioid rescue medication use will be calculated as the time from end of surgery to time of event in hours. Missing NRS scores at timepoints of interest will not be imputed. Subjects with missing NRS values at the timepoint of interest will be excluded from the summary.

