15.6.3.2 Secondary Efficacy Measures

The secondary efficacy measures will be analyzed using a hierarchical fixed-sequence stepwise testing procedure. To protect the Type 1 error rate, the testing will be performed in a sequentially rejective fashion. If the first test is significant at the 0.05 level, then, and only then, the next secondary efficacy measure will be tested, and so forth. The results will be declared statistically significant at the 0.05 significance level.

Continuous Measures of Efficacy

For the AUC of pain intensity scores, missing data will be imputed as described in [Section 15.5](#) and fully described in the SAP.

For the integrated rank assessment that uses total amount of postsurgical opioids consumed through 48 hours, opioid medications will be converted to an IV morphine equivalent amount. All opioids consumed through 48 hours will be included in the analysis.

Summary statistics for each measure will be shown at each timepoint by treatment group. To test for significant differences between EXPAREL and placebo with respect to continuous measures of efficacy, an ANOVA with treatment as the main effect will be used. Based on the model, EXPAREL will be compared to placebo and two-sided CIs about the difference will be presented.

Categorical Measures of Efficacy

For categorizing subjects as pain-free, the NRS pain intensity score must be 0 or 1 at the assessed timepoint.

The proportion of subjects in each category will be calculated and summarized at each timepoint by treatment group. A chi-square test or Wilcoxon Rank Sum test will be used to compare EXPAREL to placebo.

Time to Event Measures of Efficacy

The time from start of study drug administration to the first use of an opioid rescue medication through 96 hours will be summarized with Kaplan-Meier estimates. A log-rank test will be used to compare EXPAREL to placebo.

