7.6.2.3.7. Time to First Opioid Rescue Medication

The number and percentage of subjects ever and never using opioids after surgery through 72 hours will be presented by treatment. Subjects who did not take opioids will be censored at the time of discharge from the clinic or from the time of withdrawal, whichever is sooner. The 25th (first quartile), 50th (median – second quartile) and 75th (third quartile) percentiles, minimum and maximum time to first use of opioid rescue medication will be estimated using Kaplan-Meier methods. The quartile and the 95% confidence limits for each quartile will be presented by treatment. This summary will be presented overall and for each site.

A Kaplan-Meier plot of the time to first rescue medication use will be presented.

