| Time Point | Pain Free | Statistic | EXPAREL [N=XX] | Placebo [N=XX] |
|------------|-----------|-----------|----------------|----------------|
| 15 min | No | n (%) | xx (xx.x) | xx (xx.x) |
| | Yes | n (%) | xx (xx.x) | xx (xx.x) |
| 30 min | No | n (%) | xx (xx.x) | xx (xx.x) |
| | Yes | n (%) | xx (xx.x) | xx (xx.x) |
| 1 hour | No | n (%) | xx (xx.x) | xx (xx.x) |
| | Yes | n (%) | xx (xx.x) | xx (xx.x) |
| Etc. | No | n (%) | xx (xx.x) | xx (xx.x) |
| | Yes | n (%) | xx (xx.x) | xx (xx.x) |

Pain-free is a NRS score of 0 or 1 with no prior rescue medication use.

Source: list SAS datasets used to create table
SAS X.Y

DDMONYYYYTHH:MM
program_name

Note to programmer: Do not split time point across pages. Time points to appear on this tables are 15 min, 30 min and 1 hour, 2 hour, 4 hour, 6 hour, 8 hour, 12 hour, 24 hour, 48 hour, 72 hour, 96 hour and Day 10.

Pacira Pharmaceuticals (Page X of Y) Protocol: 402-C-329
Table 14.2-9: Summary of Time to First Rescue Medication Use (hours) - Primary Efficacy Analysis Set
Site: Overall

| | Statistic | EXPAREL [N=XX] | Placebo [N=XX] |
|----------------------|---------------|----------------|----------------|
| Rescued | n (%) | xx (xx.x) | xx (xx.x) |
| No Rescue (censored) | n (%) | xx (xx.x) | xx (xx.x) |
| Quartiles [1] | | | |
| First (25% rescued) | Est. (95% CI) | xxx (xxx,xxx) | xxx (xxx,xxx) |
| Median (50% rescued) | Est. (95% CI) | xxx (xxx,xxx) | xxx (xxx,xxx) |
| Third (75% rescued) | Est. (95% CI) | xxx (xxx,xxx) | xxx (xxx,xxx) |
| Minimum | Observed | xxx | xxx |
| Maximum | Observed | xxx* | xxx* |

* indicates censored observation

Est. = Point estimate; CI = confidence interval

[1] Estimates from Kaplan-Meier analysis.

Source: list SAS datasets used to create table

DDMONYYYYTHH:MM

program_name

SAS X.Y

Note to programmer: First page will present overall sites; subsequent pages will present each site - one site per page.

Pacira Pharmaceuticals

(Page X of Y)

Protocol: 402-C-329

Table 14.2-10: Summary of Integrated Rank Assessment of NRS Pain Intensity Scores and Opioid Use - By Assessment Timepoint - Primary Efficacy Analysis Set

Site: Overall

| Assessment Timepoint | Statistic | EXPAREL [N=XX] | Placebo [N=XX] |
|----------------------|--------------------|----------------|----------------|
| 24 hours | n | xx | xx |
| | Mean | xx.x | xx.x |
| | Standard Deviation | x.xx | x.xx |
| | Minimum | xx | xx |
| | Median | xx.x | xx.x |
| | Maximum | xx | xx |

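### Time to first opioid rescue carries a missing-NRS exclusion that the endpoint does not need and that conflicts with the SAP's own censoring rule

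*SAP*

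**What the plan says.** SAP 7.6.1.9 gives the derivation: "Time to first opioid rescue medication use will be calculated as the time from end of surgery to time of event in hours". Two sentences on missing pain scores follow, the second being "Subjects with missing NRS values at the timepoint of interest will be excluded from the summary".

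SAP 7.6.2.3.7 gives the analysis. It opens with "The number and percentage of subjects ever and never using opioids after surgery through 72 hours will be presented by treatment", then states "Subjects who did not take opioids will be censored at the time of discharge from the clinic or from the time of withdrawal", whichever comes first. The quartiles and their confidence limits come from Kaplan-Meier. Table shell 14.2-9 follows this plan: it is set on the primary efficacy analysis set, has one row for rescued subjects and one for censored subjects without rescue, and has no row or footnote for NRS exclusions.

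Protocol 15.6.3.2 describes the same endpoint as "The time from start of study drug administration to the first use of an opioid rescue medication through 96 hours", summarised with Kaplan-Meier estimates. It has no condition on pain scores.

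**The concern.** A time-to-event endpoint needs an origin, an event time and a censoring time. SAP 7.6.1.9 adds a condition on a fourth item, the pain score, that the endpoint does not use. A subject can have a complete rescue record and still be removed for a missed NRS assessment.

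Two programmers could follow different sections of the same SAP. The one who starts from 7.6.1.9 drops subjects; the one who starts from 7.6.2.3.7 keeps everyone in the set. They would report different denominators, quartiles and curves, and the SAP does not say which section prevails. The opioid-free percentages in 7.6.2.2 and 7.6.2.3.6 carry no NRS exclusion, so opioid use could also be reported on different samples from one table to the next.

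A smaller mismatch sits beside this one. The ever/never count in 7.6.2.3.7 stops at 72 hours, while censoring runs to discharge, which Protocol 13.5 places after the 96-hour assessments.

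**Working it through.** The plan gives no figure for this endpoint to reproduce, so the check is mainly textual. The arithmetic in steps 4 and 5 is illustrative and rests on stated assumptions.

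**1. Does the endpoint need a pain score?** No. Its inputs are the end of surgery, the time of first rescue and, for non-users, discharge or withdrawal. SAP 7.1.1.3 expects the surgery and rescue records to be complete, and that does not depend on the NRS record.

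**2. Where does the rule belong?** SAP 7.6.1.7 contains the same two sentences word for word. There they make sense, because the integrated rank uses the NRS score at 24, 48 and 72 hours. SAP 7.1.1.2 states the matching missing-data rule for that endpoint: "Subjects with missing NRS scores at the timepoints of interest will not be included in the summaries". Time to first rescue has no such timepoint, so the phrase about the timepoint of interest points to nothing. Carried-over text is the likeliest explanation.

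**3. What happens to each kind of subject?**

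| Subject | Under 7.6.1.9 | Under 7.6.2.3.7 |
|---|---|---|
| Rescued, NRS missed at the timepoint | Removed; an observed event is lost | Kept as an event |
| Not rescued, NRS missed, stays to discharge | Removed | Censored at discharge |
| Withdraws without rescue before the timepoint | Removed | Censored at withdrawal |

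The last row shows the contradiction most clearly. The withdrawal clause exists for such subjects, yet they have no later NRS scores.

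**4. How many subjects?** This cannot be derived. If 2% to 10% of subjects were affected (an assumption), the loss would be 0.02 × 175 = 3.5 to 0.10 × 175 = 17.5, or about 4 to 18 of the planned 175. The primary efficacy set holds only subjects enrolled under Amendment 2 and is smaller. At the 50 per group that Protocol 15.3 aims for under that amendment, the loss would be 2 to 10 of 100.

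**5. Which direction?** Assume exponential times to rescue with median m hours and no censoring before 24 hours. The opioid-free share at 24 hours is S = 2^(−24/m). Let a fraction d of all subjects be excluded.

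- Missingness unrelated to rescue: the share stays at S and only numbers are lost.
- All excluded subjects already rescued by 24 hours: S/(1 − d).
- All excluded subjects not yet rescued at 24 hours: (S − d)/(1 − d).

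For m = 12, S = 25.0%. With d from 2% to 10%, the second case gives 0.25/0.98 = 25.5% to 0.25/0.90 = 27.8%. The third gives 0.23/0.98 = 23.5% to 0.15/0.90 = 16.7%. For m = 48, S = 70.7%, and the two ranges are 72.2% to 78.6% and 70.1% to 67.5%.

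The SAP reports quartiles, so the median is also of interest. Take m = 12 and d = 10%. If the excluded are all unrescued at 24 hours, the new curve reaches 0.5 where the true curve is 0.5 × 0.90 + 0.10 = 0.55, at 12 × log2(1/0.55) = 10.3 hours. If they are spread evenly over those already rescued, the rescued share is multiplied by (0.65/0.75)/0.90 = 0.963. The median then falls where the true rescued share is 0.5/0.963 = 0.519, at 12 × log2(1/0.481) = 12.7 hours. These are extreme allocations, against a true median of 12.

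**6. The 72-hour count.** A first rescue at, say, 80 hours is an event on the Kaplan-Meier curve but counts as never in a tabulation through 72 hours. Protocol 15.6.3.2 follows this endpoint through 96 hours.

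**7. Time origin.** SAP 7.6.1.9 starts the clock at the end of surgery, consistent with Time 0 in SAP section 5. Protocol 15.6.3.2 starts it at the beginning of study drug administration.

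**The case against.** The strongest reply is that the analysis section, the table shell and the protocol all point to ordinary Kaplan-Meier with censoring, so a competent programmer would see the NRS sentences as stray text. Shell 14.2-9 supports this: it makes no provision for NRS exclusions, whereas the PoSSe shell 14.2-12.1 lists subjects with missing totals. This stands as far as intent goes. A reader might infer that the SAP drops these subjects in place of censoring them; the documents do not support that, because 7.6.2.3.7 does provide censoring. What remains is a stated rule in the derivation section that contradicts the rest.

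A reader might also infer a large loss. With 12 scheduled scores and an assumed 1% to 2% miss rate per score, 1 − 0.99^12 = 11.4% to 1 − 0.98^12 = 21.5% of subjects would miss at least one. That calculation takes any missed score as grounds for exclusion and treats misses as independent. SAP 7.6.1.9 speaks of a single, undefined timepoint, and subjects who leave early miss scores in runs. With one timepoint, the same assumed rate gives 1% to 2%. Subjects also stay in the facility under staff supervision for 96 hours (Protocol 13.1), which should limit missed assessments.

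The 72-hour point is narrower than it may look. Shell 14.2-9 shows no 72-hour cut, and SAP 7.6.2.3.6 already tabulates opioid use through 96 hours. What stands is one inconsistent time limit in the text of 7.6.2.3.7.

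**Conclusion.** The point holds as a contradiction within the SAP. Followed literally, 7.6.1.9 gives the wrong sample for time to first rescue, losing observed events as well as censored times. That much rests on the text alone.

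Its size is unknown. The loss of 2% to 10% of subjects is assumed, as are the exponential times and the extreme allocations behind the shifts shown. A reader might infer that bias is established because missing scores come from subjects in distress or leaving early. Neither document says so, and the shift could go either way or be nil.

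The consequence is limited. The endpoint is tertiary in both documents and outside the fixed testing sequence. SAP 7.6.2.3 plans no test on it (Protocol 15.6.3.2 plans a log-rank test), and shell 14.2-9 is not among the topline tables. The opioid-free secondary endpoints carry no NRS exclusion. No confirmatory conclusion depends on this point.

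**What to change.** - In SAP 7.6.1.9, delete the two missing-NRS sentences.
- State that every subject in the primary efficacy analysis set is included, with non-users censored at discharge or withdrawal, whichever is sooner, as 7.6.2.3.7 already says.
- In SAP 7.6.2.3.7, change the ever/never count from 72 to 96 hours, so that it matches the Kaplan-Meier follow-up and Protocol 15.6.3.2.
- Reconcile the time origin: end of surgery in SAP 7.6.1.9, start of study drug administration in Protocol 15.6.3.2. Choose one and record the reason for any departure from the protocol.

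The cost is SAP wording only. No new data, change of sample size or change to shell 14.2-9 is needed.
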